8.1.4 NIHSS

The NIHSS will be obtained prior to randomization (baseline) by an investigator who is NIHSS certified. The NIHSS will be repeated at least once daily during the treatment period, and it is strongly recommended that this be completed by a certified investigator. It is required that the Day 90 NIHSS is scored by an NIHSS certified investigator.

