8.4 Follow-up Procedure

The goal of the study is to achieve complete, accurate follow-up for the three month study period. Subjects will be contacted at 6 weeks by phone for reports of SAEs, to capture early follow up information and to make arrangements for the 3 month study follow up visit during which time the primary clinical outcome (mRS) and secondary outcomes will be captured. Any subject unable to return in person will undergo a 3 month study follow up visit by phone.

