5.2 Intent-to-Treat Sample

As the primary analysis, all efficacy and safety outcome measures will be analyzed under the intent-to-treat principle (ITT). Under this principle, the evaluable sample includes all subjects who are randomized. Each subject will be analyzed according to the treatment group to which they were randomly assigned at the time of randomization.

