10.2 Secondary Outcome Variable Analysis

This study is designed to test the primary hypothesis. However, it also offers the opportunity to conduct analyses to evaluate important additional neurological and functional outcomes using the NIHSS, BI and SSQOL. All secondary analyses will be conducted using the intention to treat study population. Favorable outcomes for the NIHSS and BI are defined as: a score of 0 or 1 on the NIHSS and a score of 95-100 on the BI at 90 days post randomization. Because there are only three secondary efficacy outcomes, adjustment for multiplicity will not be made. Each of these dichotomous outcomes will be analyzed using a chi-square test at a significance level of 0.05. With a study sample size of 1400, we have 80% power to detect absolute differences in favorable outcome for the: NIHSS of 7% (assuming control group is 25%) and BI of 8% (assuming control group is 40%). The SSQOL 90-day score will be analyzed as a continuous outcome. Mean scores overall and for each domain will be compared between the two treatment arms, adjusting the alpha level for multiple testing. Secondary analyses of all secondary outcomes will adjust for the specific covariates that are listed above in the primary analysis section as well as additional covariates identified at the time of analysis.

In addition to the above clinical outcomes, we also will examine/compare blood glucose measurements over time as well as protocol conduct metrics between treatment arms: time to target, time in target, early/late time to treatment and adherence to the computerized glucose monitoring system.

Secondary Outcome	Definition	Descriptive Statistics
Time to Target	(Randomization Time – Time Target is met (hrs)); target met defined as BG of 70-180 in the control arm and BG of 70-130 in the treatment arm.	Two-sided 95% confidential intervals; means, Comparison of means between treatment arms.
Time in Target	Blood Glucose Measurements During Treatment	Proportion of measurements out of target; area under the curve; box plots over time (every 4hrs) by treatment arm and by primary outcome.
Time to Treatment	Randomization Time - Stroke Onset Time (hrs)	Comparison of means between treatment arms.
Time on Treatment	Randomization Time – Infusion stop time (Form 15)	Comparison of means between treatment arms.

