11. SAFETY ANALYSES

11.1 Safety Monitoring

The safety monitor and DSMB will receive periodic safety reports of all adverse events and serious adverse events. Statistical monitoring for safety will be limited to subjects experiencing a severe hypoglycemia event (<40 mg/dL) during the treatment period and death rate within 90 days post randomization. It is anticipated that the respective event rates in the control arm will be 0% for severe hypoglycemia and 14% for death. For severe hypoglycemia, the absolute difference in event rates between the two treatment arms will be monitored using two-sided 95% confidence intervals. Stopping the trial due to harm will be considered if at any time the lower limit of the severe hypoglycemia interval exceeds 4%. For death rate, an unadjusted relative risk will be estimated. Stopping the trial due to harm will be considered if at any time the 95% confidence interval excludes 1. These point estimates will be provided in each DSMB Closed Report. The table below provides different scenarios of when the boundary for safety may be crossed.

Severe Hypoglycemia Events				
N per group	Total Subjects with Event in Control Arm (%)	Total Subjects with Event in Exp Arm (%)	Risk Difference (Δ)	Lower Limit of 95% CI for Δ
50	0 (0)	7 (14)	14	4.4
50	1 (2)	9 (18)	16	4.7
100	0 (0)	10 (10)	10	4.1
100	2 (2)	14 (14)	12	4.7
200	0 (0)	16 (8)	8	4.2
200	4 (2)	22 (11)	9	4.2
500	0 (0)	31 (6.2)	6.2	4.1
500	10 (2)	45 (9)	7	4.2
700	0 (0)	41 (6)	6	4.1
700	14 (2)	59 (8.4)	6.4	4.1

Death Events				
N per group	Total Subjects with Event in Control Arm (%)	Total Subjects with Event in Exp Arm (%)	Unadjusted Relative Risk	Lower Limit of 95% CI for RR
50	5 (10)	14 (28)	2.8	1.09
50	7 (14)	17 (34)	2.4	1.10
100	10 (10)	22 (22)	2.2	1.10
100	14 (14)	27 (27)	1.9	1.08
200	20 (10)	35 (17.5)	1.8	1.05

CONFIDENTIAL

200	28 (14)	45 (22.5)	1.6	1.05
500	50 (10)	74 (15)	1.5	1.06
500	70 (14)	98 (20)	1.4	1.06
700	70 (10)	99 (14)	1.4	1.06
700	98 (14)	132 (19)	1.4	1.06

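### Mean 90-day SSQOL has no rule for death or missing scores, so it becomes a survivor comparison; NIHSS and BI need a smaller clarification

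*SAP*

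**What the plan says.** **Population.** SAP 10.2: "All secondary analyses will be conducted using the intention to treat study population". SAP 5.2 defines that population: "Under this principle, the evaluable sample includes all subjects who are randomized".

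**SSQOL.** SAP 10.2: "The SSQOL 90-day score will be analyzed as a continuous outcome", and "Mean scores overall and for each domain will be compared between the two treatment arms, adjusting the alpha level for multiple testing". It gives no SD, effect size or power for SSQOL, and no value for a subject who has died.

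**NIHSS and BI.** SAP 10.2 makes both binary at 90 days (NIHSS 0 or 1; BI 95 to 100), tests each by chi-square at 0.05, and states 80% power with 1400 subjects for 7 points on NIHSS (control 25%) and 8 points on BI (control 40%).

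**Missing data.** SAP 8 specifies multiple imputation for the 90-day mRS only, from a model with 90-day mRS, treatment, baseline NIHSS, thrombolysis, age, gender and 6-week mRS. Its sensitivity analyses re-run the primary analysis only. The 3% loss figure also refers to the mRS.

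**Deaths.** SAP 11.1: "It is anticipated that the respective event rates in the control arm will be 0% for severe hypoglycemia and 14% for death".

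**Phone visits.** Protocol 8.4: "Any subject unable to return in person will undergo a 3 month study follow up visit by phone". Protocol 8.1.4: "It is required that the Day 90 NIHSS is scored by an NIHSS certified investigator". Protocol 5.2, exclusion 6, keeps out people who could not come back for the 90-day visit.

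**The concern.** A mean over all randomized subjects cannot be computed when some have died and no score is assigned to them. The natural default is the mean in those alive and assessed, reported under an intention-to-treat label.

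That comparison is no longer protected by randomization. If one arm keeps alive patients who would have died in the other, and these patients are badly disabled, they lower the SSQOL mean of the arm that saved them. The reverse also holds: an arm with more deaths can appear to have better quality of life. At stake is the direction of a secondary efficacy result that readers would take as a randomized comparison.

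A smaller gap concerns living subjects. NIHSS is an examination scale, and neither document says how it is obtained or coded after a phone visit. Inability to attend is plausibly related to disability, so those scores may not be missing at random.

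**Working it through.** **1. Expected deaths.** SAP 11.1 gives 14% in control: 0.14 × 700 = 98, which matches the 98 (14%) row for 700 per group in the SAP's own death table. If both arms had 14% (assumption), there would be 196 deaths in 1400. The 3% loss in SAP 8 corresponds to 0.03 × 1400 = 42. Death is thus the main reason for an absent SSQOL score.

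**2. The plan's power figures for the binary outcomes.** Pooled normal approximation, two-sided 0.05, 1:1 allocation:

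| Analysed per arm | NIHSS 25% vs 32% | BI 40% vs 48% |
|---|---|---|
| 700 (deaths counted as not favorable) | 82.7% | 85.5% |
| 602 (14% dropped from each arm) | 76.8% | 79.9% |

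The stated 80% for NIHSS is consistent with analysing everyone (81.2% at 700 per arm with continuity correction). The BI figure does not discriminate: at 700 per arm the detectable difference is 7.4 points, which the SAP may have rounded up to 8. The stated N of 1400 fits counting all subjects in both tests.

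**3. Size of the SSQOL shift.** Assume 14% deaths in control, a fraction 0.14 − k in the IV insulin arm, and that the extra survivors score g SD below other survivors. They form k / (0.86 + k) of that arm's survivors, so

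shift = g × k / (0.86 + k), against the arm with fewer deaths.

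Neither k nor g is in the documents.

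| Mortality difference k | g = 1.5 SD | g = 2 SD |
|---|---|---|
| 0 | 0 | 0 |
| 2 points | 0.034 | 0.045 |
| 3 points | 1.5 × 0.03/0.89 = 0.051 | 2 × 0.03/0.89 = 0.067 |
| 4 points | 0.067 | 0.089 |

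**4. Yardstick.** Detectable difference at 80% power with 600 survivors per arm: (1.96 + 0.84) × √(2/600) = 0.162 SD at unadjusted alpha 0.05. SAP 10.2 requires an adjusted alpha but does not name the method. Assuming Bonferroni over 5 to 10 tests, the multiplier becomes 2.576 + 0.842 = 3.418 to 2.807 + 0.842 = 3.649, giving 0.197 to 0.211 SD. The 3-point shift is therefore 31 to 42% of the detectable difference at unadjusted alpha, and 24 to 34% under this adjustment.

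**5. Cross-check with a different model.** Assume a normal latent score, deaths taken from the lowest scores, no other treatment effect, 700 per arm and unadjusted alpha 0.05. Equal mortality gives no shift and 5% rejection. Deaths of 14% vs 12% give 0.04 SD and about 10% rejection; 14% vs 11% give 0.059 SD and about 18%; 14% vs 10% give 0.08 SD and about 28%. This is an upper-end case, since real deaths would not all be the lowest scorers.

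**6. The opposite direction.** With 98 deaths in control and 119 (17%) under IV insulin, the relative risk is 119/98 = 1.21 with lower 95% limit 0.95, so the mortality guideline in SAP 11.1 is not met. Under the model in step 5 the survivor mean would still favor the arm with more deaths by about 0.057 SD.

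**7. NIHSS after phone visits.** The documents give no phone share, so no size can be derived from them.

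**The case against.** The strongest reply is that the SAP does say intention-to-treat. A reader might infer that all secondary efficacy comparisons run on survivors; the documents do not support that. NIHSS and BI are binary, so a death can be counted as not favorable without imputation, and their power is stated at the full 1400. What is missing for these two is one sentence of coding. SSQOL is different, because a mean has no such natural value for the dead.

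Three further limits stand. First, 14% is a control-arm figure and the SAP anticipates no mortality difference; with equal mortality the survivor mean carries no bias from death. Second, a reader might infer that phone visits remove many disabled subjects from the NIHSS test. Ability to return is an entry condition, phone is a fallback of unstated size, and procedures may be in the Manual of Procedures, which was not available. Phone visits would also select attenders, not survivors, so this is a separate problem. Third, SAP 11.2 compares mortality directly, so a survivor mean need not be read alone.

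It can also be argued that ranking death worst is a choice of estimand and not a correction. That is fair, and it is a reason to confine the rank comparison to the overall score: in every domain test it would repeat the mortality comparison. None of these points supplies the missing rule for SSQOL.

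**Conclusion.** The point holds for SSQOL. As written, the mean comparison cannot be carried out on all randomized subjects and becomes a survivor mean. It is unbiased by death if mortality is equal, and shifted against the arm with fewer deaths otherwise. The illustrative size is 0.05 to 0.07 SD for a 3-point mortality difference and a 1.5 to 2 SD deficit in those saved, both assumptions. The detectable difference is about 0.16 SD at unadjusted alpha, and larger at the adjusted alpha the SAP requires.

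For NIHSS and BI the finding is narrower: the coding of death is unstated, and living subjects seen by phone may lack an NIHSS, with unknown and possibly small frequency. Only secondary outcomes are affected. The change is worth making before unblinding but is not critical to the trial's main conclusion.

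**What to change.** Amend SAP 8 and 10.2 as follows:

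- **Overall SSQOL.** Add a prespecified rank-based comparison on all randomized subjects, with death ranked worst.
- **SSQOL means.** Keep the means, overall and by domain, but label them as comparisons among survivors and report them beside the mortality result.
- **Living subjects with missing scores.** Impute missing NIHSS, BI and SSQOL with the SAP 8 imputation model, which already contains the 90-day mRS, adding the secondary score to be imputed. This also covers an NIHSS not obtained because of a phone visit.
- **NIHSS and BI.** State that death counts as not favorable, in line with the stated N of 1400.

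The cost is a few sentences and a little programming, with no new data collection. The downside is that the rank comparison combines death with quality of life and gives no mean difference on the SSQOL scale, which is why the survivor means stay as supportive results.

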Both GRASP IV insulin doses are safe and feasible, but the tight control approach is appropriate to study in the phase III trial. GRASP data, combined with THIS trial data (target 80-130 mg/dL), the AHA guidelines (treat glucose over ~180 mg/dL), the ADA guidelines (treat over180mg/dL) and the literature reviewed above support an intervention group target glucose of 80–130 mg/dL and a control group treated with SQ insulin for glucose >180 mg/dL. Separation will be achieved as diabetics will be the study population and our preliminary data demonstrate we can adequately separate levels.

GRASP/THIS Time Window

GRASP had a 24 hour window for enrollment, but 58% of patients were enrolled <12 hours from stroke onset and 45% <9 hours. These data with the THIS trial demonstrate that patients can be enrolled within 12 hours to an acute IV insulin trial. A 12 hour window will allow tPA therapy for eligible patients, allow "wake

up stroke" enrollment and is supported by the literature. Data suggest that both inflammation and excitotoxicity likely play a major role in the injury pathophysiology that tight glucose control is interrupting. TNF alpha may be a major component of the injury pathway and is expressed by 4 hours but doesn't peak until 12 hours. A 12 hour window therefore may have greater ability to capture patients that will benefit from this therapy. The rapid sequence of evaluation and study enrollment for acute stroke patients will assure that patients will be enrolled quickly and many will likely be early in the time window (as shown in GRASP). This rapid enrollment will be maximized in our collaboration with the NETT and will allow a secondary analysis of time to treatment as we are likely to have a broad distribution of enrollment times.

GRASP/THIS Treatment Period

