5. ELIGIBILITY CRITERIA

5.1 Inclusion Criteria

- (1) Age 18 years or older
- (2) Clinical diagnosis of ischemic stroke defined as acute neurological deficit occurring in one or more cerebral vascular territories. Neuroimaging must be done to exclude intracranial hemorrhage (ICH).
- (3) Protocol treatment must begin within 12 hours after stroke symptom onset and is recommended, but not required, to begin within 3 hours after hospital arrival. If time of symptom onset is unclear or patient is awakening with stroke symptoms, the time of onset will be the time the patient was last known to be normal.
- (4) Known history of type 2 diabetes mellitus and glucose >110 mg/dL **OR** admission glucose ≥150 mg/dL in those w/o known diabetes mellitus
- (5) Baseline NIHSS score of 3-22
- (6) Pre-stroke modified Rankin Scale score = 0 for patients with an NIHSS score of 3-7. Pre-stroke modified Rankin Scale score = 0 or 1 for patients with an NIHSS score of 8-22.
- (7) Able to provide a valid informed consent to be in the study (self or their authorized legally accepted representative). The approved consent form must be signed and dated in accordance with federal and institutional guidelines.

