12.2.4 Secondary Analyses

This study is designed to test the primary hypothesis. However, it also offers the opportunity to conduct analyses to evaluate important additional neurological and functional outcomes using the NIHSS, BI and SSQOL. The secondary analyses will be conducted using the intention to treat population. In addition to these secondary clinical outcomes, the analysis

will include time to randomization from symptom onset and protocol conduct metrics between treatment arms: time to target, time in target, time to treatment and adherence to the decision support tool.

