2. SYNOPSIS OF THE STUDY

This multicenter, randomized, controlled clinical trial of approximately 1400 patients will be conducted at approximately 56 enrolling sites. Enrollment is anticipated to occur over 3.5 years. Patients will be randomly assigned to IV insulin therapy with target glucose 80-130 mg/dL or sliding scale SQ insulin (control therapy) with target glucose less than 180 mg/dL for up to 72 hours. Therapy must be initiated within 3 hours of arrival at the enrolling center and within 12 hours of stroke onset. The primary efficacy outcome will be the dichotomized mRS score at 90 days post randomization adjusted for the baseline severity of stroke (responder analysis). The primary safety outcome will be severe hypoglycemia (<40 mg/dL). Additional safety outcomes will include overall hypoglycemia (blood glucose <55 mg/dL), symptoms and signs associated with hypoglycemia, and death. Secondary outcomes include functional outcomes at 90 days, a 6 hr vs 12 hr enrollment analysis, measures of glucose control success and adherence to the computerized glucose monitoring system.

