10.1.2 Primary Efficacy Analysis at the End of the Trial

The primary outcome analysis of the 90-day mRS will use a stratified dichotomy methodology for assessing improvement as defined in the Primary Outcome section above. Outcome differences will be analyzed under the intention-to-treat principle, therefore all randomized subjects will be included in the primary analysis sample. To assess efficacy, the treatment groups will be compared with respect to the proportion with favorable outcome 90 days post randomization after controlling for the variables included in the randomization scheme. The primary statistical analysis will develop a generalized linear model using the PROC GENMOD procedure in SAS® v9 with treatment group as the factor of interest and baseline NIHSS strata (3-7, 8-14, 15-22) and thrombolysis use (Yes/No; includes both IV and IA therapies) as covariates. A Wald

[figure not shown]
chi-square test will be performed to compare the treatment group proportions using a two-tailed significance level of 0.05. Adjusted relative risks will be reported with two-sided 95% confidence intervals. Additional analyses will identify potential confounding (prognostic) variables to be used as covariates in subsequent secondary analyses of the primary outcome. Specific covariates include age, gender, race, ethnicity, admission blood glucose, previous stroke, lacunar subtype, and time between stroke onset and treatment. If statistically significant differences are evident, then post-hoc analyses will be conducted to determine if differences had an effect on the conclusions from the pre-specified primary analysis.

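### SAP 10.2 needs three corrections to its descriptive conduct metrics: Time to Treatment is measured to randomization, the Time to Target band differs from the stated target, and the comparison of means has no rule for patients who never reach target

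*SAP*

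**What the plan says.** **Time to Treatment.** The SAP 10.2 table gives it as "Randomization Time - Stroke Onset Time (hrs" and plans a comparison of means between arms. Protocol 12.2.4 names the two intervals separately; its planned secondary work "will include time to randomization from symptom onset and protocol conduct metrics between treatment arms: time to target, time in target, time to treatment". The eligibility clock in Protocol 5.1 runs to treatment: "Protocol treatment must begin within 12 hours after stroke symptom onset". The covariates for the secondary adjusted analyses in SAP 10.1.2 include "lacunar subtype, and time between stroke onset and treatment", and SAP 10.2 carries that list into the adjusted analyses of the secondary outcomes.

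**Target band.** The Time to Target row has "target met defined as BG of 70-180 in the control arm and BG of 70-130 in the treatment arm". The intervention target is 80-130 mg/dL in SAP 2 and in Protocol 2.1, 3.5 and 8.2.3.2. Protocol 8.2.3.3 starts the hypoglycemia procedure below 80 and records hypoglycemia below 70. The Time in Target row plans "Proportion of measurements out of target" and names no band.

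**Summary of Time to Target.** The row asks for means, 95% intervals and a comparison of means between arms. The imputation rules in SAP 8 concern the 90-day mRS only.

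**The concern.** A row labelled Time to Treatment that stops at randomization cannot show how quickly either strategy was started, yet a reader of the results table would take it that way. If it stays the only interval computed, the time-to-treatment metric listed in Protocol 12.2.4 is never produced.

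The 70 limit means that a reading of, say, 75 mg/dL in the intervention arm is scored as target met while it sets off the hypoglycemia procedure.

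A mean of Time to Target needs a value for every patient. Those who never reach target, or who die, are discharged or stop treatment first, have none, and the analyst's choice for them can alter the comparison.

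What is at stake is the account of whether the two glucose strategies were delivered and separated. Protocol 3.3 explains an earlier trial's uninformative result partly by both arms reaching the same glucose range, so these metrics will be read closely if the primary result is null.

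**Working it through.** The plan gives no power, alpha or expected value for these metrics, so there is no figure to reproduce. The check is a comparison of definitions, plus simple algebra.

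**1. Time to Treatment.** Let O be stroke onset, R randomization and S treatment start.
- Onset to treatment start: S - O = (R - O) + (S - R).
- The SAP row is R - O, so it omits S - R. The documents give no value for S - R.
- R - O is fixed before assignment. The assigned strategy cannot change it, so comparing it between arms only checks baseline balance. Any difference in speed of starting lies in S - R.
- The event that marks S is not obvious in the control arm: saline runs continuously (Protocol 8.2.3.1.2), but subcutaneous insulin is given only at four fixed clock times, as needed (Protocol 8.2.3.1.3).
- As a covariate, S - O falls after randomization and does not exist for patients never treated, a group that SAP 5.4 recognizes. R - O has neither problem.

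**2. Target band.**

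| Source | Intervention | Control |
|---|---|---|
| SAP 2 | 80-130 | below 180 |
| Protocol 8.2.3.1, 8.2.3.2 | 80-130 | below 180 |
| SAP 10.2, Time to Target | 70-130 | 70-180 |
| SAP 10.2, Time in Target | not named | not named |

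At the top of the control band the only conflict is the value 180 itself, which is trivial. In the intervention arm, the lower limit alters Time to Target only if a patient's first reading at or below 130 falls in 70-79, or if the reading falls below 70 and the recovery passes through 70-79. Coming from above 130, the first case needs a fall of at least 131 - 79 = 52 mg/dL between successive checks. Those checks are hourly for the first 4 hours and then about every 1 to 2 hours (Protocol 8.2.3.2.1). After a reading below 80, rechecks follow every 15 minutes until 80 is reached (Protocol 8.2.3.3), so the added delay would usually be short. The effect on this row is therefore very small. Time in Target uses every reading, so the choice of band has more room to matter there, and that row names none.

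**3. Means.** Let f be the share of an arm that never reaches target, m the mean time among those who do, and T the value given to the rest.
- Mean with everyone included: (1 - f)m + fT.
- Mean with those patients left out: m.
- Difference: f(T - m), which is positive whenever T exceeds m and grows with f. Leaving patients out therefore flatters the arm with the larger f.
- The documents give neither f nor m. T is at most 72 h (SAP 2), but setting T = 72 h is not neutral either: Protocol 3.4 expects some mild strokes to be discharged before three days, and some patients may die. No number of hours can be defended from the documents.

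**4. Starting position.** Patients with type 2 diabetes enter with glucose above 110 (Protocol 5.1). A glucose of 111-130 at randomization is in band at time zero in either arm; one of 131-180 is in band only in the control arm. The two arms face different hurdles by definition.

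**The case against.** The strongest case on the other side has four parts.

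- These rows sit under a descriptive heading, outside the three secondary efficacy outcomes. That stands, and it limits the weight of the point.
- Time to Treatment may be loose shorthand for enrollment time. Protocol 3.4 expects "a secondary analysis of time to treatment as we are likely to have a broad distribution of enrollment times", SAP 2 lists "a 6 hr vs 12 hr enrollment analysis", SAP 10.2 itself speaks of early and late time to treatment, and the schedule in Protocol 8.7 places randomization and study drug both at baseline. This is plausible. But Protocol 12.2.4 still lists two intervals, and under this reading the second has no definition.
- The 70 limit may come from the threshold for recording hypoglycemia in Protocol 8.2.3.3. It may, but no passage says so.
- The SAP does not say that patients who never reach target will be dropped, and the Manual of Procedures, which may hold a rule, was not available. Many controls may also reach target early: the GRASP control median during treatment was 151 mg/dL (Protocol 3.4). This stands as a limit on size. The missing rule in the SAP remains.

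A reader might go further and infer that the adjusted analyses rest on a faulty covariate and should use treatment start. The documents do not support that: onset to randomization is the safer covariate because it precedes assignment, and the SAP only has to say that this is what it means. A reader might also infer that the 70 limit materially inflates glucose-control success. For the one row that states the limit, it does not.

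**Conclusion.** The point holds as three defects in descriptive protocol-conduct metrics, and they are worth correcting before analysis. The primary analysis, alpha, sample size and safety monitoring are unaffected. The Time to Treatment row does not measure what its name and Protocol 12.2.4 describe; the gap equals the randomization-to-start interval, which the documents do not give. The band conflict is real on the text and very small in effect on Time to Target; its effect on Time in Target depends on a band that is not stated. The comparison of means can favour the arm with more patients who never reach target. That direction assumes they are left out, which the SAP neither says nor rules out, and the size cannot be estimated. A claim that the comparison is biased by a known number of hours, or that a known percentage of readings is misclassified, would rest on assumed inputs and should not be made.

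**What to change.** 1. **Time to Treatment.** Rename the row onset to randomization. Add a metric of treatment start minus stroke onset, state which recorded event marks the start in each arm, and report the number never treated by arm. State that the onset-to-treatment covariate in SAP 10.1.2 is onset to randomization, with the start-based interval at most a sensitivity analysis.
2. **Target band.** Reconcile the SAP 10.2 band with SAP 2 and Protocol 2.1, 3.5, 8.2.3.2 and 8.2.3.3, or state why the analysis band differs. State which band applies to Time in Target. This review does not choose a band.
3. **Time to Target.** Keep randomization as the origin and summarize by cumulative incidence of first reaching target, with death as a competing event and a stated rule for discharge and for stopping of treatment. Report by arm the number never reaching target and the number already in band at randomization. Note that the arms have different bands, so the comparison shows delivery of each strategy and is not like for like.

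**Cost.** SAP wording and programming only. Glucose values and check times appear to be captured electronically (Protocol 4.4), treatment start appears to be needed already to verify the 12-hour criterion (Protocol 5.1), and the infusion stop time is on Form 15 (SAP 10.2).
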